7.2 Presentations

- Submission of abstracts for conference presentation should be agreed in advance with the TMG. Authors should allow sufficient time for their request to be reviewed. This may be completed via email.
- However, if there is insufficient time for the TMG to review such a request, the CI can make a decision on behalf of the TMG.
- The body of the presentation (including posters) should be reviewed by the TMG prior to presentation. This may be completed via email.

7.3 Dissemination

Dissemination for the project is embedded within WP4. Dissemination activities will be manifold and will aim to reach and engage as many individuals who will be affected by or can affect change through the research findings as is feasible. Important findings will be shared with stakeholders at various stages of the project, for example via four site specific

dissemination events. The research and practitioner community will also be kept informed of key research findings, recommendations of good practice and innovations via a project e-newsletter which will be circulated at 6 monthly intervals, conference presentations, published outputs of project data within targeted journals and practitioner publications which are likely to have the widest reach, e.g. open access journals will be selected where appropriate to ensure findings are freely accessible and available as early as possible to affect change. Guides detailing how to best support and facilitate digital health participation for online health providers and ICT providers who develop digital health resources will be made freely available via a project website. In addition, an accessible report summarising findings, digital participation stories and key recommendations will be shared in order to facilitate digital health participation and will be circulated via advocacy groups (e.g. West Midlands Self Advocacy Network), networks of people with intellectual disabilities (e.g. Choice Forum) and to organisations working with people with intellectual disabilities (e.g. Foundation for People with Learning Disabilities; Learning Disability England; Mencap, BILD) and cascaded down to their members. Key findings and outputs will also be shared with press offices at each site and via social media with the intention of engaging local and national and international media with our research and raising public awareness. Also, an accessible project website will be developed.

References

- Alfredsson Ågren, K. *et al.* (2020). Digital participation? Internet use among adolescents with and without intellectual disabilities: A comparative study. *New Media & Society*, 22(12), 2128-2145.
- Amankwaa, L. (2016). Creating protocols for trustworthiness in qualitative research. *Journal of Cultural Diversity*, 23(3), 121-127.
- American Psychiatric Association. (2013). *Diagnostic and statistical manual of mental disorders* (5th ed.).

Appendix 1: Digital Health Participation of People with Intellectual Disabilities Logic Model

CONTEXT		AIMS		
Digital participation & its relationship with health literacy has seldom been considered empirically for this group. Existing measurement of digital participation & health literacy are currently inadequate for those with intellectual disabilities to enable assessment of this key healthcare quality indicator. The facilitators, barriers & outcomes of digital health participation & levels of digital health participation and inequality are currently not well understood for this population.		To determine levels of and factors which influence digital health inequity. To explore how digital health participation occurs in the lives of adults with intellectual disabilities. To explore the distribution of psychometrically valid & accessible measures of digital health participation & health literacy & via comparison with referent groups. To explore the influence of digital health participation & health literacy on levels of inequality (WP2). A diary study will also explore processes of digital health participation.		
INPUTS (resources invested)	PROCESSES		OUTCOMES	
	Activities (what is done)	Outputs (what will be achieved by activities)	Short-term	Medium-term
Project Team: PI, Site Leads, Research assistants (RAs), Co-researcher (CR) with intellectual disabilities. Partner organisation support & facilitation for project. Support from carers (paid staff & family members) & professionals. Illustrator to provide pictures to enhance accessibility of data collection & dissemination materials.	WP1. Development of Digital Health Participation Scale & focus group topic guides; Scoping review to gather existing digital participation & health literacy measures; Focus groups with people with intellectual disabilities & their carers to identify salient aspects of digital participation & health literacy. Workshops to select scale items & response formats.	Development of initial Digital health participation survey for use in WP2 and associated manual.	Co-development of an accessible, psychometrically valid measure of components of digital health participation & health literacy which can be utilised in both research & practice to better understand how digital health participation operates in the lives of people with intellectual disabilities.	Use by researchers of the psychometrically valid measure of components of digital health participation & health literacy for use as a measure of healthcare quality for a population excluded from digital inclusion. Health literacy & participation.
Financed Project Resources: iPads (& Sim cards), Laptops, ARCGIS, Qualtrics licence. Participant remuneration for time, payment for RAs, third sector partner organisations & co-researcher(s) with intellectual disabilities. PPIE Payment for steering committee members. Translation costs.	WP2. Longitudinal Digital Health Participation Survey. Collation of measures of background, social determinants of health & wellbeing alongside bespoke digital participation survey. Participants across four sites with intellectual disabilities (N=400) complete survey twice (8 month follow up). Workshop to provide survey completion training. Carers, RAs & CR to support survey completion. Quantitative analysis (Cross-lagged PA, CFA).	Analysis of psychometric properties of Digital Health Participation Survey. People with intellectual disabilities to complete survey to provide digital health participation information at two time points. Longitudinal modelling of causal factors influencing digital health participation & wellbeing of people with intellectual disabilities. Development of sampling frame from survey cohort and recruitment of sample of participants with intellectual disabilities for WP3.	Enhanced understanding of how background characteristics, social determinant of health, digital participation & health literacy interact to influence wellbeing amongst people with intellectual disabilities.	Illumination of digital health participation needs of the participants
Supervision & Training: Regarding data collection processes & methods provided to RAs and Co-researcher(s). Training, guidance & ongoing support in survey completion & use of ArcGIS storysharing software. Qualitative analysis training for RAs from PI.	WP2. Comparative survey study. Recruitment of matched referent group of people without intellectual disabilities. Completion of Digital Health Participation Survey by referent group. Comparative analysis to identify inequalities in digital health participation (GLM).	Identification of levels of inequality in digital health participation.	Enhanced understanding of levels of digital & health inequality for people with intellectual disabilities and the factors specific to people with intellectual disabilities which perpetuate & alleviate inequalities and exclusion.	
	WP3. Digital Diary study. Training of 40 participants in use of ArcGIS & use of iPads for health related activities. RA & carer support & monitoring of weekly qualitative data collection. Thematic framework analysis of collated qualitative accounts / stories.	Identification of nature and processes of support, interdependence & independence in digital health participation via qualitative diary accounts to be compiled into stories of people's day-to-day lived experiences of digital health participation.	Deeper understanding of the ways digital health participation operates in the lives of people & the barriers & facilitators of participation and good practice in supporting digital health participation.	Greater awareness of digital health participation possibilities by people with intellectual disabilities & those involved in WP3.
	WP4. Dissemination & Output Co-creation activities. Write up of findings. Solution focussed workshops with all stakeholders to identify next steps & develop preliminary intervention components to ameliorate barriers to digital health participation	(i) Guides detailing how to support & facilitate digital health participation for (ia) people with intellectual disabilities; (ib) carers / online health providers; (ic) digital health resource developers; (ii) Accessible report summarising findings, digital participation stories & recommendations; (iv) Final 'Digital Health Participation' survey.	Enhanced evidence about digital health participation of people with intellectual disabilities. Development of a suite of interventions from this work that sit alongside natural supports to be evaluated in future research work following funding.	Providers of digital health ICT platforms will be required to make adaptations needed to support people with intellectual disabilities. Empirical evidence to guide research, social care & health policy.
ASSUMPTIONS			EXTERNAL FACTORS	
Digital health exclusion: People with intellectual disabilities are at risk of digital exclusion and reduced opportunity to engage in health decision making due to reduced health literacy. Much health provision and information are now delivered digitally, thus people with intellectual disabilities are doubly disadvantaged in relation to ongoing involvement in their health. Measurement Development: It is possible to co-create a psychometrically valid measure of digital health participation for completion by people with intellectual disabilities.			Support for Participants to complete data collection: Completion of data collection is reliant for many participants on the support of their carer(s) and the value of health decision making. Also the health of individual participants may be impacted by data collection.	

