2.4.1 Longitudinal Survey Study

The digital participation survey (Proxy or Self/supported completion as appropriate) will be administered to a convenience sample of 400 people with intellectual disabilities at two time points eight months apart (+/-1 month). This sample size will enable digital health participation for people with intellectual disabilities to be adequately understood across the breadth and heterogeneity inherent in this population. It will also enable a sufficiently powered analysis to identify moderate effect sizes in relation to predictors of digital health participation.

Survey sampling & recruitment

Adults with a diagnosis of intellectual disabilities and the family and paid carers (as proxy participants for people with higher support needs) are the target population. Taking a whole population approach, and to increase geographical diversity, a self-selecting sample of 400 adults with intellectual disabilities will be recruited equally from the four study sites.

Recruitment will be facilitated by partner organisations with established groups of people with intellectual disabilities and links with additional community groups and agencies which contain under-represented groups of people with intellectual disabilities. Birmingham Community Healthcare NHS Foundation Trust will also act as a recruitment centre. Our overall planned accrual rate is 50-60 participants per month across the four study sites (12-15 per site) over seven months to reach our aim of a final sample size of 400 (Note we expect some of the 60 participants from WP1 to participate in WP2 and WP3).

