Partner organisations will ensure adequate oversampling to offset participant drop out. The organisations will also support sample replenishment in the case of non-completion of the survey at time 1. Levels of dropout in longitudinal studies with individuals with intellectual disabilities is approximated at 13% (McCarron *et al.*, 2020); however, we will conservatively allow for up to 15% via oversampling (McCarron *et al.*, 2020). To ensure inclusion of under-represented groups (e.g. people with intellectual disabilities from: ethnic minority/global majority groups, with autism, who are older, and who have underlying physical health problems) and groups more at risk of digital exclusion (older; unemployed; living in group settings supported by paid staff; people with greater support needs (via carers) (Anrijs *et al.*, 2022), sample characteristics will be reviewed after 25% of initial survey data collection has been achieved. If insufficient at initial recruitment, a purposive/targeted sampling strategy, facilitated by partner organisations, will be implemented to ensure adequacy of representation. This review process will be repeated once 75% of initial survey data collection is complete.

Longitudinal survey data collection

Prior to data collection, participants and their carers will be invited to attend online training workshops provided within the project to support the survey data collection (Work package 2). Training will be provided by the CI and site/regional PIs alongside the RAs and the CRs with intellectual disabilities.

Participants will choose their preferred modality for survey completion (Paper-based, online completion (housed on Qualtrics), telephone completion, face-to-face completion as an interview with the geographically closest researcher or a known carer). Where appropriate, the survey will be administered by RAs and CR at each study site. Self and carer supported completion will also be offered for data collection. Survey methods are viable for use with people with intellectual disabilities and have been used successfully by applicants previously and in recent large-scale studies (e.g. Caton *et al.*, 2022). Guidance on completion will be

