2.4.2 Comparative study of Digital Health Inequality

A cross sectional comparative study will contrast digital health participation of people with intellectual disabilities to a reference group people without disabilities.

Comparator

A reference group of 200 participants without disabilities will be recruited across the study sites via local advertisement and social media. This referent group will concurrently complete the same Digital Health Participation survey online via Qualtrics. A referent sample of 200 will allow detection of a group difference, $d=0.2812$ (small-medium effect) at 90% power, 2:1 group ratio, and $\alpha=0.05$. Sample size calculations were conducted using G*Power 3.1.9.7. Our overall planned accrual rate for the referent group is 25-30 participants per month across the four study sites (6-8 per site) over seven months to reach our aim of a final sample size of 200.

Primary outcome

Digital health participation levels as developed from the work in WP1 will be used as the primary outcome measure.

Secondary outcome

Level of mental and physical wellbeing will be measured using the EQ5 (Herdman *et al.* 2011).

Comparative study statistical analysis

Descriptive analysis of levels and frequency of digital health participation of the groups (N=600). Between group comparison using general linear model (GLM) of digital health participation of people with intellectual disabilities.

The study will use propensity score weighting (inverse probability weights) to reduce the bias due to confounding variables and ensure sufficient balance across groups. The propensity scores will be generated on the basis of the following variables: geographic region, sex, age band, ethnicity, and deprivation index. In the event that models including the probability weights do not converge, we will explore other approaches to resolve (i.e. direct adjustment as the number of covariates is relatively small).

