3.2 Inclusion and exclusion criteria

3.2.1 Inclusion criteria

We have two main participant groups for the study which are detailed below with their respective inclusion criteria:

1. People with intellectual disabilities

- Has a diagnosis of intellectual disabilities
- Over 18 years of age
- Has capacity to give informed consent
- Has a carer or family member able to support participation in the relevant aspect of the study (if this is necessary for the participant to successfully take part)

2. Carers of people with intellectual disabilities

- Providing daily support to people with intellectual disabilities who are unable to consent to participate in research.

3. Adults without intellectual disabilities (Referent Group)

- For WP2 we will also recruit a third group of participants who will be the comparison referent group. The criteria for inclusion for these participants is that they are an adult, have the capacity to consent to take part and do not have intellectual disabilities.

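### The referent group is called matched in Appendix 1, but section 2.4.2 sets no matching rule and nothing checks during accrual that referents overlap with the intellectual-disability sample

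*Protocol*

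**What the plan says.** Appendix 1, under the WP2 comparative survey study, lists "Recruitment of matched referent group of people without intellectual disabilities".

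The operative sections describe something else:

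- **Recruitment (2.4.2):** "A reference group of 200 participants without disabilities will be recruited across the study sites via local advertisement and social media". No matching variables, matching ratio or quotas on personal characteristics are given.
- **Eligibility (3.2.1):** a referent qualifies if "they are an adult, have the capacity to consent to take part and do not have intellectual disabilities".
- **Accrual:** the referent target in 2.4.2 is "25-30 participants per month across the four study sites (6-8 per site) over seven months"; the intellectual-disability target in 2.4.1 is "50-60 participants per month across the four study sites (12-15 per site) over seven months". This is the only alignment at recruitment, and it concerns region.
- **Balance (2.4.2):** inverse probability weights from a propensity score on region, sex, age band, ethnicity and deprivation index, with direct adjustment as an example of what to try if the weighted models do not converge.
- **Composition review (2.4.1):** "sample characteristics will be reviewed after 25% of initial survey data collection has been achieved", and "This review process will be repeated once 75% of initial survey data collection is complete". The under-represented groups it gives as examples are "people with intellectual disabilities from: ethnic minority/global majority groups, with autism, who are older, and who have underlying physical health problems"; it also covers groups at greater risk of digital exclusion. If representation is insufficient, targeted sampling through the partner organisations follows. Section 3.1 describes the reach reviews in the same terms. Neither section applies them to referents.

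**The concern.** There are two linked problems. First, Appendix 1 and section 2.4.2 disagree on what kind of comparator the study has. A reader of the logic model would expect similarity to be built in at recruitment; the methods section leaves it to the analysis.

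Second, monitoring is one-sided. Age and ethnicity are among the characteristics that may be steered in the intellectual-disability sample, and both are propensity variables. Referents are whoever answers the advertisements, and their make-up is not looked at during accrual. The planned weights can only redistribute the people who were recruited. If some part of the covariate range is thin among referents, a few of them carry large weights, or the model extrapolates. The stated fallback responds to non-convergence, yet a weighted model can converge with poor overlap.

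At stake is the contrast that delivers secondary aim (iv) and the inequality part of the primary aim. Who was recruited is settled within the seven-month accrual, so a later analysis plan cannot repair it.

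**Working it through.** **1. The plan's own figure.** Inputs from 2.4.2: 200 referents, 2:1 ratio (so 400 with intellectual disabilities), d=0.2812, alpha 0.05, power 90%.

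Normal approximation, two-sided: power = Φ(d / √(1/n_ref + 1/n_ID) − 1.96).

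With 200 and 400: √(1/200 + 1/400) = 0.0866; 0.2812 / 0.0866 = 3.247; power = Φ(1.287) = 90.1%. The noncentral t gives 90.0%. The figure reproduces as a two-sided, unweighted comparison of independent groups. There is no arithmetic error.

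**2. Cost of weighting.** The Protocol gives no composition for either group, so the following are assumptions: one binary covariate, such as an older age band, held by share p of the intellectual-disability sample and share q of referents.

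If a group of size n with share s is weighted to a target share P, its effective size is n / [P²/s + (1−P)²/(1−s)].

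*Both groups weighted to the pooled 400:200 sample*, so P = (400p + 200q)/600:

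- p=50%, q=20%: P = 0.40. Referents: 200 / (0.16/0.2 + 0.36/0.8) = 200/1.25 = 160. Intellectual-disability group: 400 / (0.16/0.5 + 0.36/0.5) = 400/1.04 = 385.
- p=50%, q=10%: P = 0.367. Referents: 200 / (1.344 + 0.446) = 200/1.790 = 112. Intellectual-disability group: 400 / (0.269 + 0.802) = 400/1.071 = 373.

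*Referents weighted to the intellectual-disability sample*, so P = p and that group stays at 400:

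- 50% vs 20%: 200 / (0.25/0.2 + 0.25/0.8) = 200/1.5625 = 128.
- 50% vs 10%: 200 / (0.25/0.1 + 0.25/0.9) = 200/2.778 = 72.

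Putting these sizes into the power formula at d=0.2812:

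| Assumed shares | Weighting target | Effective referents | Power |
|---|---|---|---|
| equal | either | 200 | 90% |
| 50% vs 20% | pooled | 160 | 85% |
| 50% vs 10% | pooled | 112 | 74% |
| 50% vs 20% | intellectual-disability sample | 128 | 79% |
| 50% vs 10% | intellectual-disability sample | 72 | 59% |

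Section 2.4.2 does not name the target. Weighting to the pooled sample is the ordinary reading of inverse probability weights. The calculation ignores any precision gained if the covariate also predicts the outcome.

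**3. What could still be steered.** If referents accrue in parallel, the 25% and 75% points fall at about 50 and 150 of 200. About 150 and then 50 referents would remain to be recruited, so a check at these points can still change the outcome.

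**The case against.** The wording conflict is one word in a summary table. Section 2.4.2 never claims matching; it describes an unmatched comparison balanced by weighting, which is a legitimate design. That limits the weight of the contradiction but does not remove it.

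A reader might infer that the two recruitment rules necessarily drive the groups apart. The documents do not support this. Targeted sampling is conditional on the review finding representation insufficient. If the convenience sample starts short of older or minority-ethnic people, enrichment may bring it closer to the referents. Of the steered characteristics, only age and ethnicity are propensity variables; autism, physical health problems, employment, living setting and support needs are not.

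A reader might also infer that every combination of age, ethnicity and deprivation must contain referents, or that the contrast is left unadjusted. Neither holds. Propensity weighting needs overlap in the score, only an overall group contrast is planned, and the five variables are adjusted for. Overlap diagnostics and trimming belong in the analysis plan that the Protocol defers.

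The practical objection to strict matching also stands. Five variables create more joint cells than 200 people can fill, and closing cells in an online survey would need pre-screening, including a postcode look-up for deprivation.

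What remains is that referent composition is not checked during accrual, and that no analysis can add people who were not recruited.

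**Conclusion.** The point holds as a documentary contradiction and a gap in recruitment monitoring. Appendix 1 says matched; section 2.4.2 does not match, and approximate per-site accrual is the only balance at recruitment. The reviews at 25% and 75% do not cover referents. Enrichment of one group by age and ethnicity may widen or narrow the difference, and the documents do not show which.

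The size depends on unknown composition. On the assumed single-covariate differences, power falls from 90% to about 85% or 74% with pooled weights, and further if referents are weighted to the intellectual-disability sample. With equal composition nothing is lost. The sample size calculation is correct for what it assumes. The findings do not show that the comparison is invalid or that N=200 is wrong; they support an inexpensive improvement that should be made before or during accrual.

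**What to change.** In section 2.4.2, add that at the same 25% and 75% points referents are tabulated against the accrued intellectual-disability sample on the marginal distributions of region, sex, age band, ethnicity and deprivation, and that remaining advertising is directed towards under-represented margins. Set no hard caps on joint cells. Keep N=200 and the weighting, which then handles the remaining imbalance.

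In Appendix 1, replace matched with wording such as: referent group, recruitment monitored for comparability and balanced by propensity weighting.

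The cost is the Protocol wording, one extra table at each of two reviews already scheduled, and possibly slower recruitment of the last referents. No additional participants are needed.
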